The ablation will be planned and the ablation applicators inserted percutaneously using routine FDG PET/CT and possible supplemental US guidance. The ablation will then be performed using current protocols with either microwave ablation or cryoablation devices. Microwave ablation and cryoablation devices offer complimentary advantages that enable us to safely and effectively treat many liver tumors. Cryoablation may be better tolerated and less painful when ablating liver tumors close to the liver capsule or diaphragm. The iceball created during cryoablation is usually well visualized during the ablation, which can offer safety advantages when ablating near critical structures. Microwave ablation has fewer tendencies to induce thrombocytopenia or myoglobinemia than cryoablation, which can be an advantage in patients with baseline thrombocytopenia or renal insufficiency. Microwave ablation is better able to overcome vascular heat-sink phenomena that can limit the ablation of tumor cells abutting large blood vessels. Our standard practice is to choose the most appropriate ablation technology based on the individual patient's specific circumstances. Radiofrequency ablation is not included in this protocol, as microwave ablation has almost completely replaced the use of radiofrequency ablation in our practice.

[figure not shown]
When the initial ablation is completed, intra-procedural AP-PET-1 (research scan #1) will be performed and the findings recorded. Specifically, the ablation margin separating the FDG-avid tumor from the normal ammonia-perfused liver will be assessed for visibility and thickness along the entire circumference. Patients with adequate renal function (EGFR >60) will then undergo intra-procedural contrast-enhanced CT, as is now performed in routine clinical practice to monitor initial results. Non-contrast CT will be used in cases of inadequate renal function or contrast allergy. If no additional overlapping ablation applications are deemed necessary or appropriate based on routine CT (Pathway 1), the procedure will be concluded at this point. AP-PET information may be used to aid the margin assessment if CT is inconclusive. Note that routine CT will always be used to determine the safety of additional overlapping ablation, per routine clinical practice. This is because proximity of ablation devices to critical structures can only be imaged with CT and not with PET. The patient will then undergo routine 24-hour post-procedure liver MRI

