CONFIDENTIAL

This document is confidential. Do not disclose or use except as authorized.

or CT. If the CT scan suggests an inadequate ablation margin of less than 5-10 mm at any portion of the tumor surface, additional ablations will be applied to the under-treated areas (Pathway 2), if deemed safe and appropriate based on standard clinical practice. Then, AP-PET-2 will be repeated (research scan #2). Not more than two AP-PET scans will be performed during the entire procedure. The AP-PET scan(s), illustrated schematically below, constitute the only research component of the protocol.

Arm 2: Arm 2 will not include the option of AP-PET 2 (research scan #2) due to the longer half-life of FDG.

The devascularized ablation zone contains trapped high tumor FDG activity and low ablation margin FDG activity, whereas normal liver is perfused with high activity ¹³N-ammonia. The relatively photopenic ring around the tumor confirms the presence of an adequate ablation margin.

For patients with FDG-avid tumors, visibility rates of the entire ablation margin using AP-PET-1 will be compared to the visibility rates of the entire ablation margin using the intra-procedural CECT scan. Visibility rates using AP-PET-1 will also be compared to the visibility rates using the intra-procedural CECT scan fused to FDG PET (FDG PET/CECT). The concordance rates of the final intra-procedural AP-PET (research scan #1 or #2) with gold standard 24-hour post-procedure MRI or CT will be determined.

For those patients with non-FDG-avid tumors, retrospective software fusion of AP-PET-1 with pre-procedural MRI or CT will be used to assess visibility rates of the ablation margin and will be compared with visibility rates of the ablation margin using retrospective fusion of the intra-procedural CECT and pre-procedural MRI or CT. Similarly, in patients with non-FDG-avid tumors the concordance rate of final intra-procedural AP-PET (research scan #1 or #2) fused to pre-procedural MRI or CT, with gold standard 24-hour post-procedure MRI or CT will be determined. The analysis of AP-PET utility in patients with non-FDG-avid tumors is a secondary objective of this study, but is nevertheless of interest, as AP-PET may prove valuable in these patients who cannot receive IV contrast or

CONFIDENTIAL

This document is confidential. Do not disclose or use except as authorized.

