14. STATISTICAL CONSIDERATIONS

14.1 Study Design/Endpoints

Arm 2: Study design/endpoints are identical for Arms 1 & 2.

In this study of patients with liver lesions, it is expected that roughly two-thirds of patients will have FDG-avid tumors, one-third of patients will have non FDG-avid tumors, and although it is possible for a patient to have both types of tumor, that is considered rare. For sample size and power considerations we therefore conservatively assume that patients will have one type of tumor or the other and therefore target a sample size of 100 patients per arm, allowing for the potential for renal insufficiency in up to 25% of all patients (described in more detail below). Also, as the techniques focus on analysis by tumor and it is estimated that 70% of patients will have only a single lesion, the sample size considerations will focus on enrolling *patients* rather than *tumors*. Multiple tumors per patient, when they occur, will be treated and assessed in the statistical analysis, with appropriate adjustment for clustering of tumors within a patient to account for correlation of responses within a patient. Sample size considerations, however, focus on enrollment of patients. The study design and endpoints are identical for Arm 1 and Arm 2.

Primary Objectives:

1. Among FDG-avid liver tumors, comparison of imaging techniques will be done on paired tumor samples using McNemar's test, focusing on discordant pairs (AP-PET-1 adequate/CECT inadequate and AP-PET-1 inadequate/CECT adequate). For these comparisons it is expected that the rate of discordance will be high (near 60% of all pairs) and that differential in discordance will be large (difference between discordant pairs on the order of 50% or higher). In addition to comparing discordant pairs, there is interest in being able to precisely estimate the visibility rates under each imaging modality. With 50 paired samples in the FDG-avid liver tumor ablation group in each arm, visibility of the entire ablation margin can be estimated with a 95% binomial confidence interval that should be no wider than 24 percentage points (+/- 12%) in the expected range of visibility of each modality (80% for AP-PET and 20% for CECT). This sample size will provide greater than 90% power for McNemar's test using a 5% type I error given the assumptions above about discordance.

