Within arm, comparison of local tumor progression rates to ablation margin adequacy will be largely descriptive as this study does not have adequate power to make definitive conclusions about progression rates. Given the expected heterogeneity of the treated liver tumor populations at presentation and potential variability in clinical follow-up for local progression, this objective is therefore largely exploratory. Intra-procedural IV iodinated contrast is not required for patients analyzed for this objective. An independent radiologist will perform blinded reads for both the final intraprocedural AP-PET and 24-hour MRI or CT to classify cases as adequate or inadequate with respect to the ablation margins for both imaging techniques. Cases will be followed clinically for at least 3-12 months to identify local tumor progression. The method of Kaplan and Meier will be used to estimate the censored time-to-failure distributions for local tumor progression with the goal of estimating, in a preliminary and exploratory fashion, the local tumor progression rates by adequacy of the blinded AP-PET and 24-hour MRI or CT reads. Statistical

CONFIDENTIAL

This document is confidential. Do not disclose or use except as authorized.

precision will be limited for these evaluations and no formal comparison of groups will be performed.

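### For the primary visibility comparisons, chiefly Objective 1, the plan does not assure that CECT is scored independently of AP-PET-1

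*Combined protocol and SAP*

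**What the plan says.** Section 1.1 fixes the live order: "When the initial ablation is completed, intra-procedural AP-PET-1 (research scan #1) will be performed and the findings recorded". The recorded findings include visibility and thickness of the margin around the whole tumor. Patients with adequate renal function "will then undergo intra-procedural contrast-enhanced CT, as is now performed in routine clinical practice to monitor initial results". The text then turns to whether more ablation is needed, and there it states that "AP-PET information may be used to aid the margin assessment if CT is inconclusive".

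Section 14.1 tests Objective 1 with McNemar's test, "focusing on discordant pairs (AP-PET-1 adequate/CECT inadequate and AP-PET-1 inadequate/CECT adequate". Objective 4 also has McNemar's test. For Objective 2, section 1.2 calls for a comparison and discordance rates, while section 14.1 plans binomial confidence intervals only.

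For non-FDG-avid tumors (Objective 4), section 1.1 says that "retrospective software fusion of AP-PET-1 with pre-procedural MRI or CT will be used to assess visibility rates of the ablation margin", with the comparator assessed "using retrospective fusion of the intra-procedural CECT and pre-procedural MRI or CT". It does not describe the FDG-avid reads as retrospective, and section 1.2 speaks of visibility during the ablations.

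On blinding, section 14.1 says under the secondary objective: "An independent radiologist will perform blinded reads for both the final intraprocedural AP-PET and 24-hour MRI or CT". Sections 1.1 and 1.3 agree. No section names the reader, the read order or any blinding for the AP-PET-1, CECT or FDG PET/CECT scores used in the primary objectives.

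**The concern.** A paired comparison of two imaging techniques measures what each shows on its own only if each is scored without the other. Here the AP-PET-1 result exists, and is recorded, before there is a CECT to read.

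CECT margin assessment is a matter of judgement: section 1.1 describes it as usually an estimate from side-by-side comparison, often without confidence around the full circumference. A reader who knows AP-PET-1 might see a margin on CECT because AP-PET showed one, which shrinks the difference. A reader who expects AP-PET to do better (section 14.1 anticipates 80% against 20% visibility) might mark CECT down, which inflates it.

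The plan provides a blinded independent reader for an exploratory analysis without formal group comparison, but specifies none for the comparison it tests. What is at stake is the meaning of the primary difference and of the CECT visibility rate.

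**Working it through.** **Inputs, all from section 14.1.** Objective 1: 50 pairs per arm, discordance near 60%, difference between the discordant cells about 50 points. Objective 4: 25 pairs, 70%, 60 points. Type I error 5%; sidedness is not stated, so two-sided is used. Stated power is above 90% for both.

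**Cell probabilities.** Let b be the share of pairs visible on AP-PET only and c the share visible on CECT only.
- Objective 1: b + c = 0.60 and b − c = 0.50, so b = 0.55, c = 0.05.
- Objective 4: b + c = 0.70 and b − c = 0.60, so b = 0.65, c = 0.05.

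**Formula.** The number of discordant pairs m is Bin(n, b + c). Given m, the AP-PET-only count x is Bin(m, b/(b + c)). The exact test rejects when 2·P[Bin(m, ½) ≤ min(x, m − x)] ≤ 0.05. Power is the rejection probability averaged over m.

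**Plan's figure first.** Exact power is 99.9% for Objective 1 and 98.4% for Objective 4. Both meet the stated 90%.

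**Carry-over toward agreement (assumed).** A fraction f of AP-PET-only pairs is scored visible on both, so b becomes b(1 − f).

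| | f | b | Difference (points) | Exact power |
|---|---|---|---|---|
| Objective 1 | 0 | 0.55 | 50 | 99.9% |
| | 0.25 | 0.4125 | 36.25 | 98.2% |
| | 0.50 | 0.275 | 22.5 | 78.6% |
| Objective 4 | 0 | 0.65 | 60 | 98.4% |
| | 0.25 | 0.4875 | 43.75 | 87% |
| | 0.50 | 0.325 | 27.5 | 53% |

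The Objective 4 rows apply only if whoever does the retrospective CECT fusion read also knows AP-PET-1.

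**Effect on the estimate.** In Objective 1 the CECT visibility rate rises by f × 55 points: 0.25 × 55 = 13.75, or 0.50 × 55 = 27.5. The plan wants that rate to within ±12 points, so the smaller shift already exceeds the stated precision while power stays at 98%.

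**Expectation in favour of AP-PET (assumed).** Take no true difference, n = 50, and let 10 or 20 points of both-visible pairs be scored as AP-PET only.
- Start from 10% discordant each way: rejection goes from 2.2% to 17.9% (b = 0.20, c = 0.10) or 54.7% (b = 0.30, c = 0.10).
- Start from 30% each way, which matches the plan's 60% discordance: rejection goes from 3.0% to 9.9% (b = 0.40, c = 0.30) or 29.9% (b = 0.50, c = 0.30).

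The result depends heavily on the assumed discordance, so neither pair of figures is a forecast.

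**The case against.** The strongest reply is that the sentence about inconclusive CT governs management, not scoring. It stands among the rules on whether to ablate further, and it presupposes that a CT judgement has already been made. A CECT that is inconclusive about the margin has arguably already failed complete circumferential visibility. CT in that paragraph also includes non-contrast CT, and patients without contrast (about 25% by the plan's estimate) supply no McNemar pair. So the inconclusive cases cannot be equated with the AP-PET-only discordant pairs. All of this stands.

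It does not close the gap. The treatment decision turns on margin adequacy on CT, section 14.1 labels the Objective 1 pairs as adequate or inadequate, and no other CECT endpoint read is described. Nothing keeps the live assessment, aided or not, from becoming the score.

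Three further points stand. Objective 4 uses retrospective fusion on both sides, so scan order alone does not contaminate it, although blinding is unspecified there too. McNemar's test allows correlated pairs, so the test itself is valid. The bias fractions are assumptions that no section supplies, and at 25% carry-over Objective 1 still exceeds its planned power.

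A reader might infer that the primary reads are unblinded, or that the plan directs CECT to be scored with AP-PET's help. The documents support neither: they are silent on blinding of these reads, and they state no such scoring rule.

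**Conclusion.** The point holds as a gap in specification: independence of the CECT and AP-PET-1 scores is not assured. It is clearest for Objective 1, where the reads appear to be live. It extends to Objective 2, whose discordance rates need the same protection although section 14.1 names no test. It applies more weakly to Objective 4.

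The bias could run either way and its size is unknown. On the assumed 25% or 50% carry-over, Objective 1 power falls to 98% or 79%, and the CECT rate shifts by 13.75 or 27.5 points. No stated power, sample size or interval width is wrong because of this. The change should be made because it protects the primary estimate, not because contamination has been shown.

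**What to change.** Add to section 14.1:
- For Objective 1 (McNemar), Objective 2 (visibility rates and discordance) and Objective 4 (fused reads), the endpoint visibility scores for AP-PET-1 and for CECT or fused CECT come from stored images.
- Each is read without the other: perfusion images are withheld from the CECT and fused CECT reads, and CECT from the AP-PET-1 reads. FDG PET remains part of the Objective 2 comparator by design.
- The reads take place in separate sessions, in an order varied across patients, by the independent radiologist already named there.
- Any live assessment aided by AP-PET goes in a separate REDCap field that the primary comparisons do not use.

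The live scan order and the operator's use of AP-PET in care stay as written. Locking the CECT score before showing AP-PET-1 to the same reader is not an adequate substitute. It moves the carry-over to the AP-PET-1 read and conflicts with the record-first order in section 1.1.

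The cost is reading time at planned numbers: about 50 CECT, 50 fused PET/CECT and 25 fused CECT reads per arm (50 + 50 + 25 = 125), plus matching AP-PET-1 reads where AP-PET-1 is not already the blinded final scan. The existing blinded read classifies adequacy, so it needs a visibility item. No new scan or reader is required. Because the reads use stored images, this can still be done although the front sheet records closure to accrual in March 2018.

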1. OBJECTIVES

1.1 Study Design - Abstract

Arm 2: This study has two arms. Arm 1 is the protocol as written below using Ammonia perfusion PET to assess ablation results of standard FDG PET/CT-guided liver tumor ablations. Arm 2 is the identical protocol, but substitutes the radiopharmaceutical FDG for Ammonia to assess ablation results of standard FDG PET/CT-guided liver tumor ablations. Arm 2 will not include the option of performing a second intra-procedural perfusion PET scan. FDG is FDA-approved for oncologic imaging as in this study. No IND or IND exemption is required. The protocol is identical in all other respects. All protocol comments pertaining to Arm 2 will be placed in new paragraphs beginning with “Arm 2:” in bold letters. Throughout the protocol, Arm 2 simply substitutes FDG for N-13 ammonia. In Arm 2, All AP-PET scans (which are the only research intervention of the study) are performed using FDG instead of N-13 ammonia.

Arm 1 and Arm 2 are independent and no randomization or enrollment criteria for one arm or the other are defined.

[figure not shown]

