- Current techniques for intra-procedural assessment of tumor ablation margins have limitations. For example, when performing CT-guided ablations, it is standard practice to obtain an intra-procedural contrast-enhanced CT (CECT) to monitor whether the tumor is being treated fully and an adequate ablation margin is being obtained following thermal ablation. CECT is usually performed only once near the end of the procedure since one dose of IV contrast material is usually the limit for a 24-hour period. If a reduced dose of IV contrast is used, this may allow for two intra-procedural CECT scans, however, this may limit the effectiveness of the method. For example, the degree of liver enhancement is reduced making it difficult to distinguish tumor from liver. Patients with a contrast material allergy or severe renal insufficiency (EGFR < 30) are often not considered candidates for CECT. An additional limitation of CECT in the assessment of liver tumor ablations is that once ablated, the tumor is usually difficult to distinguish from the surrounding ablated normal liver tissue. Consequently, direct visualization of the ablation margin is often not possible using CECT. US is even less effective in assessing ablation results in that tumor visibility is rapidly obscured by the developing ablation zone and the ablation zone margins are usually indistinct. For liver tumors, MRI performs better in depicting not only the exact borders of the ablation zone, but also in showing the residual tumor. As a result, 24-hour follow-up MRI with contrast can be an effective method for confirming the thickness or size of the ablation margin. Follow-up MRI, however, does not allow for intra-procedural assessment of ablation results during US, CT, or PET/CT-guided ablations that might prompt immediate further treatment while the patient is still on the scanner table.
- An effective imaging technique for monitoring ablations that can be safely performed repeatedly during ablation procedures is needed.
- We have previously shown that, during PET/CT-guided tumor ablation procedures, tumor FDG activity is not dissipated by thermal ablation, whether through heating or freezing (2). Tumor FDG activity remains unperturbed following ablation allowing for continued excellent PET visibility of the tumor for hours after the procedure. This unique feature of PET imaging can potentially be used to help monitor the thickness of the ablation zone

CONFIDENTIAL

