depicted as a “cold” rim would either be absent or incomplete, indicating an inadequate ablation margin. AP-PET would be obtained using a radiopharmaceutical administration protocol identical to our standard cardiac practice. PET image acquisition will be obtained dynamically, as the N-13 ammonia is injected intravenously, using 15 second frames over 5 minutes.

- The advantages of using AP-PET to define the adequacy of the ablation zone margin include a very low radiation dose to the patient, substantially less than a diagnostic CT scan and approximately one-tenth the dose from FDG PET, using equal administered activity (9). AP-PET is thus an ideal intra-procedural monitoring method that can be used repeatedly. Incorporating CECT into the PET/CT protocol could be used to assess the ablation zone margin relative to the FDG-avid tumor, but is subject to the problem of misregistration of the PET and CT images (3). In other words, the PET and CT components of a PET/CT scan are acquired at different time points and may not line up perfectly with each other, for example, due to respiratory motion between the PET and CT scans. Using FDG PET to visualize the ablated tumor and AP-PET to visualize the perfused tissue eliminates the issue of misregistration, since both are imaged at the same time and in the same position using a single PET scan.
- **Arm 2:** The advantages of using FDG as the perfusion agent for the AP-PET scan include that it does not require an on-site cyclotron – thus the technique has the potential for wide applicability. FDG is used in clinical practice during tumor ablation procedures in a split-dose fashion, dividing a standard dose into two parts: one for the targeting phase of the procedure and one for the final assessment phase of the procedure. This keeps the total radiation dose within that of a standard diagnostic PET/CT scan.
- Our Nuclear Medicine physicists at BWH have performed a PET/CT phantom study (see images below) that created compartments simulating the expected radioactivity concentrations in normal liver, the ablation margin, and the tumor that support the potential of AP-PET to demonstrate the ablation margin of FDG-avid tumors even with acquisitions as short as 30 seconds. The ablation margin appears as a dark ring around the FDG-avid tumor. Surrounding normal liver remains perfused by activity.

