- **This study will assess the rates of complete ablation margin visibility using AP-PET alone in comparison to CECT alone or fused PET/CECT. This study will assess the concordance of final intraoperative assessment of tumor ablation results using AP-PET with results observed on gold standard 24-hour contrast-enhanced MRI or CT.**
- **Patients may benefit from participation in this study if AP-PET can be used to identify an inadequate ablation margin not evident on CECT or in patients who cannot undergo CECT and are scanned without contrast. In such cases, additional overlapping ablations may be performed during the same procedure and thus increase the chance of technical success (complete tumor ablation rate) and technique effectiveness (low local recurrence rate). The safety of any additional ablation applications would be based on routine intraoperative CT scans per standard practice.**

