4.3 General Guidelines for Other Participating Institutions - N/A

4.4 Registration Process for Other Participating Institutions - N/A

5. TREATMENT PLAN

The treatment plan for this study involves the non-therapeutic administration of a radiopharmaceutical, N-13 ammonia, one to two doses, during the tumor ablation procedure. The N-13 ammonia perfusion PET scan is a diagnostic imaging test. The tumor ablation procedure is performed according to our standard clinical practice and is not itself a research activity. The use of N-13 ammonia to image liver perfusion with a PET scanner is the research portion of the procedure. The patient will receive one or two doses of N-13 ammonia (10 mCi/dose) for intra-procedural assessment of ablation results. Not more than two doses will be administered and one or both doses will be administered on the day of the tumor ablation procedure only.

Arm 2: FDG is used instead of N-13 ammonia for the research PET scan. Only one Perfusion PET scan with FDG will be performed. The FDG dose will be divided, using 8-12 mCi for targeting and 2-5 mCi for the perfusion scan. The total FDG dose will not exceed a standard FDG dose (≤ 15 mCi) used for routine diagnostic PET/CT scans or interventional PET/CT procedures.

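### In Arm 2 the only perfusion scan precedes any further ablation but is scored against a 24-hour image taken after it, with no rule for re-ablated tumours

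*Combined protocol and SAP*

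**What the plan says.** Section 1.1 sets the order of events: "When the initial ablation is completed, intra-procedural AP-PET-1 (research scan #1) will be performed and the findings recorded". Intra-procedural CT follows. If CT suggests too thin a margin, "additional ablations will be applied to the under-treated areas (Pathway 2), if deemed safe and appropriate based on standard clinical practice", and Arm 1 then repeats the perfusion scan as research scan #2.

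Arm 2 drops the repeat. Section 1.1 states that "Arm 2 will not include the option of AP-PET 2 (research scan #2) due to the longer half-life of FDG", and section 5 that "Only one Perfusion PET scan with FDG will be performed". For the rest, section 1.1 says of Arm 2: "The protocol is identical in all other respects". Section 1.2 gives the missing scan #2 as the only exception to shared objectives, and section 14.1 declares design and endpoints the same in both arms.

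Objectives 3 (FDG-avid) and 5 (non-FDG-avid) call for concordance of the final AP-PET, whether scan #1 or #2, with 24-hour MRI or CT as gold standard. For each arm, section 14.1 plans a 95% interval for concordance no wider than 24 points with 75 cases (Objective 3) and 36 points with 33 cases (Objective 5). It expects concordance of 50–80% and about 5% of cases labelled inadequate after AP-PET. It also plans an exploratory check that inadequate reads are confirmed at 24 hours and, as a secondary objective, exploratory local progression rates by AP-PET adequacy.

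**The concern.** A concordance rate measures the accuracy of a scan only if scan and reference look at the same thing. In Arm 2, a tumour ablated again after its scan has an AP-PET of the earlier zone and a 24-hour image of the enlarged one. If AP-PET correctly shows an inadequate margin and the margin is then treated, the 24-hour image shows an adequate margin and the case counts against AP-PET. If AP-PET misses an inadequate margin that CT finds and the operator treats, the case counts as agreement.

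These are not incidental cases. Section 2.3 gives as the route to patient benefit that AP-PET reveals an inadequate margin, so that "additional overlapping ablations may be performed during the same procedure and thus increase the chance of technical success". In Arm 2, the more often this happens, the lower the measured concordance. Confirmation of inadequate reads and progression by AP-PET adequacy have the same mismatch, since treatment falls between the read and the outcome.

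**Working it through.** **1. Which zone each image shows, following section 1.1 as written**

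| | Arm 1 final AP-PET | Arm 2 final AP-PET | 24-hour MRI/CT |
|---|---|---|---|
| No further ablation (Pathway 1) | after initial ablation | after initial ablation | after initial ablation |
| Further ablation (Pathway 2) | after further ablation (scan #2) | after initial ablation (scan #1) | after further ablation |

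Only the Arm 2, Pathway 2 cell is mismatched. Sections 1.2, 14.1 and 14.5 give no exclusion, separate analysis or choice of image for it.

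**2. The plan's own precision figures**

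At 50% concordance the Wald half-width is 1.96 × √(0.25/n).
- n = 75: 11.3 points, width 22.6; exact (Clopper-Pearson) width 23.6. Stated limit 24.
- n = 33: 17.1 points, width 34.1; exact width 35.7. Stated limit 36.

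Both figures reproduce.

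**3. Effect on concordance, relative to a rescan**

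Let f be the share of tumours re-ablated, q the share of those truly inadequate at the scan, and s the share of those corrected. Let Se be the probability that AP-PET reads an inadequate margin as inadequate, and Sp the probability that it reads an adequate margin as adequate. Assume an error-free 24-hour reference and the same Se and Sp before and after re-ablation. A corrected tumour agrees with the reference with probability 1 − Se without a rescan and Sp with one. Hence

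bias = −f × q × s × (Se + Sp − 1).

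The documents give none of these inputs. Taking q = 0.5 and s = 0.9:
- f = 10%: −1.35 points (Se = Sp = 0.65) to −2.70 (Se = Sp = 0.80).
- f = 20%: −2.70 to −5.40 points.

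**4. Upper limit from the plan's 5%**

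Since Sp ≤ 1, the loss is at most f × q × s × Se. Since f × q × Se cannot exceed the share read inadequate, the loss is at most s times that share. At 5% this is 5.0 points (s = 1) or 4.5 points (s = 0.9), which is 0.05 × 75 = 3.75 cases or 0.05 × 33 = 1.65 cases at s = 1.

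**5. Do the examples in step 3 fit the 5%?**

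They do not. If 5% of the other tumours are inadequate, true inadequacy at f = 10% is 0.1 × 0.5 + 0.9 × 0.05 = 9.5%. Inadequate reads are then 0.095 × 0.80 + 0.905 × 0.20 = 25.7%, or 37.9% at Se = Sp = 0.65. At f = 20% they are 28.4% and 39.2%. The examples show how the bias behaves; they do not estimate it.

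**6. Is the 5% itself firm?**

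Section 14.1 expects 95% of cases to be nominally adequate, with at least 90% of those confirmed at 24 hours. Inadequacy at 24 hours is then at most 5% + 95% × 10% = 14.5%. A discordant case must be inadequate on at least one image, so AP-PET inadequate reads must be at least the discordance minus 14.5%:
- 80% concordance: 20 − 14.5 = 5.5%.
- 50% concordance: 50 − 14.5 = 35.5%.

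The stated concordance range therefore needs more inadequate reads than 5%, and the 5-point limit is not secure.

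**The case against.** **The limitation is disclosed.** Section 1.1 gives the half-life of FDG as the reason for omitting scan #2, and section 1.2 repeats the exception beside the objectives. That stands as a description of the procedure. It does not say what the concordance rate means for a tumour treated after its scan.

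**The affected analyses are mostly descriptive.** Concordance is estimated without a test, confirmation of inadequate reads is called largely exploratory, and progression has no formal comparison. The arms are independent and no between-arm test is planned. This confines the harm to interpretation within Arm 2. Concordance is nevertheless what section 1.2 lists as primary Objectives 3 and 5.

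**The effect may be small.** On the plan's 5% it lies within the planned precision. That stands, subject to step 6 of the working.

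**A stronger reading is tempting.** Section 2.3 describes the split FDG dose as "one for the targeting phase of the procedure and one for the final assessment phase of the procedure". A reader might infer that the documents contradict each other on when the Arm 2 scan takes place, and that the McNemar comparisons in Objectives 1, 2 and 4 could also pair images of different zones. The documents do not support this. The sentence describes clinical practice and dose splitting, and a final assessment phase also fits a scan done after the initial ablation. Sections 1.1 and 1.2 remove only scan #2, which leaves the single scan in the scan #1 position. Objectives 1, 2 and 4 name AP-PET-1, which section 1.1 places directly before the contrast-enhanced CT. A mismatch there would need a late scan with an early, unrepeated CT, but section 2.3 says "CECT is usually performed only once near the end of the procedure since one dose of IV contrast material is usually the limit", which does not clearly support an early one. Figures missing from the extracted text may also show the timing. What remains is wording to reconcile.

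**Conclusion.** The point holds for Arm 2 tumours ablated again after their only scan. For them, concordance under Objectives 3 and 5, the exploratory confirmation of inadequate reads and the exploratory progression rates by AP-PET adequacy do not measure AP-PET accuracy, and the plan has no rule for them.

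The size cannot be fixed, because the re-ablated share is not stated. The limit of 5 points rests on the 5% of inadequate reads and on the assumptions in step 3, and the plan's own concordance range makes that 5% doubtful. The conclusion also assumes that the sequence in section 1.1 was followed.

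A reader might further infer that the stated goal of Objectives 3 and 5 in section 14.1, 24-hour confirmation among nominally adequate cases, is biased. That is not claimed: nominal adequacy there is judged on all available post-ablation intra-procedural imaging, not on AP-PET alone.

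**What to change.** 1. From procedure records, flag each tumour that had ablation after its last AP-PET.
2. Report Arm 2 concordance, confirmation of inadequate reads and progression by AP-PET adequacy overall and separately by that flag. Do not interpret the re-ablated stratum as AP-PET accuracy.
3. In sections 1.2 and 14.1, qualify for these analyses the statement that the two arms are the same.
4. As a minor point, reconcile the Arm 2 dose-splitting text in section 2.3 with the sequence in section 1.1. If any Arm 2 scan was in fact done after further ablation, also flag the pairs in Objectives 1, 2 and 4 whose contrast-enhanced CT preceded that ablation.

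The front sheet records permanent closure to accrual, so for enrolled patients only data extraction, analysis and reporting can change. Changes to the protocol text need an amendment with IRB approval (section 13.1).

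The statistical cost is precision. At an assumed 20% re-ablated share, the exact 95% interval near 50% widens from 23.6 to 26.4 points for Objective 3 (75 to 60 cases) and from 35.7 to 40.1 for Objective 5 (33 to 26 cases), ignoring clustering. These are planned counts; actual numbers after early closure may be lower. The stratum without later ablation is also selected on CT-judged adequacy, so it will hold few inadequate margins. For that reason the overall estimate should stay alongside it.
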